### **8.3.2. Neurologic Examination**

A general neurologic examination will be performed by the Investigator, Sub-Investigator, or designee at the scheduled visits (Section 1.3). The general neurologic examination includes assessments of the following systems: mental status, cranial nerves, deep tendon reflexes, power/strength, sensation, muscle fasciculations, and muscle atrophy.

### **8.3.3. Height and Weight**

Body weight will be measured in pounds or kilograms. Height will be measured in inches or centimeters (Section 1.3).

### **8.3.4. Vital Signs**

- Body temperature (°C or °F), pulse rate, respiratory rate, and systolic and diastolic blood pressure (mm Hg) will be assessed (Section 1.3).
- Blood pressure and pulse measurements will be assessed seated with a completely automated device. Manual techniques will be used only if an automated device is not available.
- Blood pressure and pulse measurements should be preceded by at least 5 minutes of rest for the patient in a quiet setting without distractions (eg, television, cell phones). Ideally, the same arm for each patient should be used for measurements.

### **8.3.5. Electrocardiograms**

- Single 12-lead electrocardiogram (ECG) will be performed at protocol specified visits in the SoA (Section 1.3) using an ECG machine to obtain heart rate and measures of PR, QRS, QT, and corrected QT intervals.
- Patients must be supine for approximately 5 to 10 minutes before ECG collection and remain supine but awake during ECG collection. For patients who are unable to remain supine, the ECG procedure may occur in an inclined or seated position.

- The Investigator or Sub-Investigator will be responsible for reviewing the ECG to assess whether the ECG is within normal limits and determine the clinical significance of the results. These assessments will be recorded in the source documents and the eCRF.

### **8.3.6. Patient Safety Card**

Before the first dose of study drug, a Patient Safety Card will be provided to patients to carry with them at all times. The card is provided to increase patient awareness of the risk of infections, especially meningococcal infection, and to promote quick recognition and disclosure of any potential signs or symptoms of infection experienced by patients during the course of the study and to inform patients on what actions must be taken if they are experiencing signs or symptoms of infection.

At each visit throughout the study, the study staff will ensure that the patient has the Patient Safety Card (Section 1.3).

### **8.3.7. Prior and Concomitant Medication Review**

It is important for Investigators or a designee to review each medication the patient is taking before starting the study and at each visit (Section 1.3).

#### **8.3.7.1. Prior Medications**

Prior medications and/or vaccines (including vitamins, herbal preparations, and those discussed in the exclusion criteria [Section 5.2]) and procedures (any therapeutic drug, such as surgery/biopsy or physical therapy) that the patient takes or undergoes within 30 days before the start of screening or during the Screening Period before the first dose of study drug, as well as any meningococcal vaccine administered within the last 3 years, will be recorded in the patient's eCRF. Additionally, all medications or therapies ever used for treating ALS before the first dose of study drug must be collected.

#### **8.3.7.2. Concomitant Medications**

Concomitant medications (including any medication, vitamin, herbal preparation or supplement) and procedures (defined in Section 6.5) are those received on or after the first study treatment date (Day 1), including those started before Day 1 and continued after Day 1. At each study visit, patients should be questioned about any new medication or non-drug therapies or changes to concomitant medications and nondrug therapies since the last visit. Concomitant medications and non-drug therapies should be recorded in the source documents and the patient's eCRF.

Concomitant medications must be recorded in the patient's source document/medical chart and eCRF along with:

- Reason for use
- Dates of administration including start and end dates
- Dosage information including dose and frequency

Information regarding the use of ALS specific treatment including riluzole and edaravone must be collected. Meningococcal vaccination and antibiotics administered for prophylaxis of meningococcal infection (if applicable) will also be recorded.

Any concomitant medication deemed necessary for the patient's care during the study, or for the treatment of any AE, along with any other medications, other than those listed as disallowed medications in Section 6.5.1.3, may be given at the discretion of the Investigator. However, it is the responsibility of the Investigator to ensure that details regarding all medications are recorded in full in the patient's source document/medical chart and eCRF.

The Medical Monitor should be contacted if there are any questions regarding concomitant or prior therapy.

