### 9.4.4. Prior and Concomitant Medications

For analysis and reporting purpose, any medication started prior to first dose of study drug will be considered as prior medication and any medication taken by a patient that overlaps with the intake of study drug will be considered as concomitant medication. All prior and concomitant medications including ALS-specific medications during the study, if any, will be summarized.

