**6.1.5. Prior and Concomitant Medications / Therapies**

Prior medications are defined as medications with a start date occurring before the first study dose of the RCP. Concomitant medications (RCP) are defined as medications taken during RCP, i.e., either with a stop date after the first study dose of RCP or ongoing during RCP. Concomitant medications (OLE) are defined as medications taken during OLE, i.e., either with a stop date after the first study dose of OLE or ongoing during OLE.

Medications will be coded using the WHODrug Dictionary version in use at the time of the analysis. The number (%) of participants using prior and concomitant medications will be summarized based on the WHO Anatomical Therapeutic Chemical Level 3 Class code and

generic name for FAS. All meningococcal vaccinations and prophylactic antibiotic medications after receiving meningococcal vaccine for subjects who initiated study drug will be listed separately as well.

Nonpharmacologic therapies and procedures will be reported by treatment group and overall for the SS using SOC and PT.

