##### If the start date is partial:

1. If only the day is missing
  - 1.1. If the year coincides with that of the first study drug administration date, then do the following:
  - 1.2. If the month does not coincide with that of the first study drug administration date, then impute the missing day as “01”.
  - 1.3. If the month coincides with that of the first study drug administration date
    - 1.3.1. If the end date is greater than the first study drug administration date, then impute the missing day as the day of the first study drug administration date
    - 1.3.2. If the end date is less than or equal to the first study drug administration date, then impute the missing day as the day of the end date of medication.
  - 1.4. If the year and the month do not coincide with those of the first dose date, then impute the missing day as “01”.
2. If both day and month are missing:
  - 2.1. If the year does not coincide with that of the first study drug administration date, then impute missing month as “01” and missing day as “01”.
  - 2.2. If the year coincides with that of the first study drug administration date
    - 2.2.1. If the end date is greater than the first study drug administration date, then impute the missing day and month as those of the first study drug administration.

2.2.2. If the end date is less than or equal to the first study drug administration date, then impute the missing day and month as those of the end date of the medication.

2.3. If the start date is completely missing, the missing start date will be set as the earlier of the first study drug administration date and end of the medication date.

For meningococcal vaccination, the missing end date will not be imputed.

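### Applied to dates, SAP 6.1.5 puts a drug that both starts and stops on Day 1 in neither the prior nor the concomitant medication table

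*Protocol*

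**What the plan says.** Two protocol sections and one SAP section define the classes.

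- Protocol 8.3.7.2, on what is collected: concomitant medications are "those received on or after the first study treatment date (Day 1), including those started before Day 1 and continued after Day 1". For timing, the record holds "Dates of administration including start and end dates"; no clock time is requested.
- Protocol 9.4.4, on analysis and reporting: a drug begun ahead of the first dose is prior. For the other class the rule is: "any medication taken by a patient that overlaps with the intake of study drug will be considered as concomitant medication".
- SAP 6.1.5, on the tables: "Prior medications are defined as medications with a start date occurring before the first study dose of the RCP". For the other class, "Concomitant medications (RCP) are defined as medications taken during RCP", which the same sentence spells out as "either with a stop date after the first study dose of RCP or ongoing during RCP". The OLE definition has the same form, with the first OLE dose as the boundary.

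SAP 6.2.2 fills in incomplete medication dates by comparing them with the date of first study drug administration. One of its rules reads "If the end date is less than or equal to the first study drug administration date, then impute the missing day as the day of", and goes on to name the medication's end date.

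**The concern.** The protocol's collection definition includes Day 1. The SAP's two tests both stop short of it: one needs a start before the first dose, the other a stop after it. A drug taken on Day 1 only sits exactly on the boundary.

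Such records concern treatment given around first exposure, for example a one-day drug given for a reaction to the first infusion. SAP 5.6.2 counts adverse events from the first dose onward, uses the clock time of onset where available, and tabulates infusion reactions separately. An infusion reaction on Day 1 would therefore appear in the adverse event tables while the drug used to treat it could be absent from both medication tables. The same strict boundary is used at the first OLE dose, which for patients randomised to placebo is the first dose of ravulizumab.

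**Working it through.** The plan states no figure to reproduce; the check is a truth table.

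**Inputs.** Let D1 be the date of the first RCP dose, s the start date and e the stop date of a medication.

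- SAP 6.1.5 prior: s < D1.
- SAP 6.1.5 concomitant (RCP): e > D1, or ongoing.
- Protocol 8.3.7.2 concomitant: e ≥ D1, or ongoing.

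**Why dates.** Protocol 8.3.7.2 asks for medication dates only. Protocol 6.4 does record the time of each study drug dose, but without a medication time there is nothing to compare it with. SAP 6.2.2 compares dates throughout and has no clock-time rule like the one for adverse events in SAP 5.6.2.

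**Boundary case.** Put s = e = D1. Prior: D1 < D1 is false. SAP concomitant: D1 > D1 is false, and the drug is not ongoing. Protocol 8.3.7.2: D1 ≥ D1 is true.

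**All patterns.** The third column shows the SAP result if clock times were available.

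| Medication | SAP, dates | SAP, clock times | Protocol 8.3.7.2 concomitant? | SAP with stop on or after D1 |
|---|---|---|---|---|
| Day 1 only, before infusion | neither | prior | yes | concomitant |
| Day 1 only, after infusion | neither | concomitant | yes | concomitant |
| Start Day -5, stop Day 1 before infusion | prior | prior | yes | prior and concomitant |
| Start Day 1, stop Day 2 | concomitant | concomitant | yes | concomitant |
| Start Day -5, stop Day -1 | prior | prior | no | prior |
| Start Day 1, ongoing | concomitant | concomitant | yes | concomitant |
| Day 10 only | concomitant | concomitant | yes | concomitant |

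Only the first two rows leave a record in neither table. Protocol 9.4.4 leaves neither of them out: a Day 1 drug that overlaps study drug intake is concomitant, and one started before the dose is prior.

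**Imputed records.** In SAP 6.2.2, with end date = D1:

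- Rule 1.3.2 (day of start missing, month and year as for D1) sets s = D1.
- Rule 2.2.2 (day and month missing, year as for D1) sets s = D1.
- Rule 2.3 (start wholly missing) takes the earlier of D1 and the end date, so s = D1.

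Each produces s = e = D1, so a drug that may have begun earlier leaves the prior table as well. By contrast, when both dates are wholly missing, SAP 6.2.2 counts the drug in both classes.

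**OLE boundary.** Let W be the date of the first OLE dose, with W > D1, and put s = e = W. RCP test: W > D1 is true, so the drug is RCP-concomitant. OLE test: W > W is false, so it is not OLE-concomitant. The record stays in a table, but only the one for the earlier period.

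**The case against.** The strongest reply is that SAP 6.1.5 refers to the first dose, not its date, and opens with "Concomitant medications (RCP) are defined as medications taken during RCP". A drug given for a first-infusion reaction is taken during the RCP and does stop after that dose began, so it is lost only if the rule is programmed on dates. This is fair as to intent, and it shows that the SAP does not mean to exclude such drugs. It does not settle the matter: the clause after the lead words is the operational test, it refers to a stop date, and the protocol requests no medication times that would let a program do otherwise.

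A second reply is that Protocol 8.3.7.2 governs collection, and 9.4.4 is the direct comparator for analysis. This stands in part. Under 9.4.4, a drug begun earlier and finished on Day 1 before the infusion is correctly prior only. But 9.4.4 gives no support for leaving a Day 1 drug out of both tables.

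A reader might infer more than the documents support:

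- *Vaccines and prophylactic antibiotics go missing.* Meningococcal vaccinations and post-vaccination prophylactic antibiotics are listed separately under SAP 6.1.5. Under Protocol 8.1.2 the required prophylaxis runs from the first day of study drug until 2 weeks after a vaccination given less than 2 weeks earlier, so it ends after Day 1 and passes the SAP test.
- *The data disappear altogether.* SAP 5.1 provides by-patient listings, and infusion reactions have their own tables and listing.
- *Drugs given on the OLE switch day are lost.* They are in the RCP table.
- *A known number of patients is affected.* Taking 1% to 5% of the planned 354 would give 3.5 to 17.7 patients, but neither rate has any source in the documents. A ceiling of 118 placebo patients at the OLE boundary (354 ÷ 3) would need full enrolment and every placebo patient reaching Week 50. The study stopped for futility, and SAP 6.4 describes the OLE data as few.

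**Conclusion.** The point holds as a boundary error in a descriptive rule. Every record with start and stop on Day 1, whether recorded or imputed, falls in neither summary table, although Protocol 8.3.7.2 counts it as concomitant and 9.4.4 does too when it overlaps study drug intake. At the OLE boundary the effect is attribution to the RCP alone.

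This rests on one assumption: that the SAP rule is applied to calendar dates, as the recorded data and SAP 6.2.2 imply. With clock times, a drug given only on Day 1 after the infusion would be concomitant and one given only before it would be prior.

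The size is small and cannot be put as a patient count. No efficacy, exposure or adverse event rule in the SAP uses the classification. The point is a minor correction.

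**What to change.** In SAP 6.1.5, define concomitant (RCP) as *stop date on or after the date of the first RCP dose, or ongoing*, and concomitant (OLE) as *stop date on or after the date of the first OLE dose, or ongoing*. Naming the date also settles whether the comparison is with the dose or with its day.

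In the table under the working, this changes only the three patterns that end on Day 1. A drug given only on the day of the first OLE dose would appear in both the RCP and the OLE tables. The imputation rules in SAP 6.2.2 can stay as they are, because a record they set to Day 1 would then be tabulated as concomitant.

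The cost is a few words and one comparison operator per period. SAP section 1 has this amendment finalised before the final database lock, so it fits as a clarification before lock. The downside is that a drug finished on Day 1 before the infusion also counts as concomitant. That matches Protocol 8.3.7.2 but is slightly broader than the overlap wording of 9.4.4, and the SAP should say so.

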### **8.3.8. Clinical Safety Laboratory Assessments**

- See Section 10.2 for the list of clinical laboratory tests to be performed and the SoA (Section 1.3 for the timing and frequency).
- The Investigator must review the laboratory report, document this review, and record any clinically relevant changes occurring during the study in the AE section of the eCRF. The laboratory reports must be filed with the source documents. Clinically significant abnormal laboratory findings are those which are not associated with the underlying disease, unless judged by the Investigator to be more severe than expected for the patient's condition.
- All laboratory tests with values considered clinically significantly abnormal during participation in the study or within 8 weeks after the last dose of study drug should be repeated until the values return to normal or baseline or are no longer considered clinically significant by the Investigator or medical monitor.
  - If such values do not return to normal/baseline within a period of time judged reasonable by the Investigator, the etiology should be identified and Alexion notified.
  - All protocol-required laboratory assessments, as defined in Section 10.2, must be conducted in accordance with the Laboratory Manual and the SoA.
  - If laboratory values from non-protocol specified laboratory assessments performed at the institution's local laboratory require a change in patient management or are considered clinically significant by the Investigator (eg, serious adverse event (SAE) or AE or dose modification), then the results must be recorded in the CRF.

### **8.3.9. Suicidal Ideation and Behavior Risk Evaluation**

Patients being treated with a study drug for a neurologic indication should be evaluated prospectively for suicidal ideation or behavior during the study.

In this study, the Columbia-suicide severity rating scale (C-SSRS) will be used to monitor suicidal ideation and behavior. The Baseline/Screening version (Section 10.11) will assess lifetime risk as well as risk in the past 12 months. Intervention-emergent suicidal ideation and behavior will be monitored using the C-SSRS-Since Last Visit version (Section 10.12).

The C-SSRS will be performed by the Investigator or an appropriately trained designee at visits specified in the SoA (Section 1.3) to ensure that patients who are experiencing suicidal thoughts or behavior are properly recognized and adequately managed or referred for further evaluation. Additional C-SSRS assessments are permitted as needed.

### **8.3.10. Pregnancy**

Pregnancy testing must be performed on all WOCBP at protocol-specified time points in the SoA (Section 1.3). Pregnancy tests (local urine testing will be standard unless serum testing is required by local regulation or IRB/IEC) may also be performed at any time during the study at the Investigator's discretion.

WOCBP must have a negative pregnancy test (serum if required per country regulations) before study drug administration.

- Details of all pregnancies in female patients and, if indicated, female partners of male patients will be collected after the start of study drug and until the termination of the pregnancy.
- If a pregnancy is reported, the Investigator should inform Alexion within 24 hours of learning of the pregnancy and should follow the procedures outlined in Section 10.4.
- Abnormal pregnancy outcomes (eg, spontaneous abortion, fetal death, stillbirth, congenital anomalies, ectopic pregnancy) are considered SAEs. Pregnancy alone is not considered an AE.
- If a patient becomes pregnant, the study drug must be immediately discontinued, and Alexion must be notified as per Section 10.4. Each pregnancy will be followed to term and Alexion notified regarding the outcome (Section 10.4.3).

## **8.4. Adverse Events and Serious Adverse Events**

The definitions of AEs and serious SAEs are specified in Section 10.3.

Adverse events will be reported to the Investigator by the patient (or, when appropriate, by a caregiver, surrogate, or the patient's legally authorized representative).

The Investigator and any qualified designees are responsible for detecting, documenting, and recording events that meet the definition of an AE or SAE and remain responsible for following up AEs that are serious, considered related to the study drug or study procedures, or that caused the patient to discontinue the study drug (Section 7).

### **8.4.1. Time Period and Frequency for Collecting AE and SAE Information**

All AEs and SAEs will be collected from the signing of the ICF until the last visit specified in the SoA (Section 1.3).

All SAEs will be recorded and reported to Alexion or designee immediately and under no circumstance should this exceed 24 hours, as indicated in Section 1.3. The Investigator will submit any updated SAE data to Alexion within 24 hours of awareness.

Investigators are not obligated to actively seek AEs or SAEs after conclusion of the study participation. However, if the Investigator learns of any SAE, including a death, at any time after a patient has been discharged from the study, and he/she considers the event to be reasonably related to the study drug or study participation, the Investigator must promptly notify Alexion.

#### **8.4.2. Method of Detecting AEs and SAEs**

The method of recording, evaluating, and assessing causality of AEs and SAEs and the procedures for completing and transmitting SAE reports are provided in Section 10.3.

Care will be taken not to introduce bias when detecting AEs and/or SAEs. Open-ended and non-leading verbal questioning of the patient is the preferred method to inquire about AE occurrences.

#### **8.4.3. Follow-up of AEs and SAEs**

After the initial AE/SAE report, the Investigator is required to proactively follow each patient at subsequent visits/contacts. All SAEs and AEs of special interest (AESI; as defined in Section 8.4.5) will be followed until resolution, stabilization, the event is otherwise explained, or the patient is lost to follow-up (as defined in Section 7.3). Every effort will be made to undertake protocol-specified safety follow-up procedures. Further information on follow-up procedures is provided in Section 10.3.

#### **8.4.4. Regulatory Reporting Requirements for SAEs**

- Prompt notification by the Investigator to Alexion of a SAE is essential so that legal obligations and ethical responsibilities towards the safety of patients and the safety of a study drug under clinical investigation are met.
- The Sponsor has a legal responsibility to notify both the local regulatory authority and other regulatory agencies about the safety of a study drug under clinical investigation. The Sponsor will comply with country-specific regulatory requirements relating to safety reporting to the regulatory authority, IRB/IEC, and Investigators.
- Suspected unexpected serious adverse reactions must be reported according to local regulatory requirements and Sponsor policy and forwarded to Investigators as necessary.
- An Investigator who receives an Investigator safety report describing a SAE or other specific safety information (eg, summary or listing of SAEs) from Alexion will review and then file it along with the Investigator's Brochure and will notify the IRB/IEC, if appropriate according to local requirements.

